8.2 Tolerability endpoint analysis

Cohort: Injection population

Analysis description: Number and percent of participants who receive at least 1 injection and who discontinue receiving injections prior to the full course of injections due to intolerance of injection or burden of study procedures. Reasons for intolerance may include:

- a. Injection site reaction
- b. Burden of study procedure
 - i. Participant refused further participation
 - ii. Participant is unwilling or unable to comply with required study procedures
 - iii. Participant refused further study product use
 - iv. Participant unable to adhere to visit schedule

8.3 Acceptability endpoint analysis

8.3.1 Completion of scheduled injections

Population: Injection population and Enrolled population

Analysis description: Number and percent of participants who complete all scheduled injections¹

¹Definition of completing all scheduled injections for participants who are confirmed HIV positive or discontinue product due to the following reasons:

- Death
- Early study closure
- HBV infection

During Step 1:

Enrolled population: completed all 0 of 0 scheduled injections

Injection population: not applicable, did not receive injection

During Step 2:

Both enrolled and injection populations: completed all injections whose target window closed prior to death/seroconversion/product discontinuation date

8.3.2 Preferred method for HIV prevention

Population: Injection population

Analysis description: Number and percent of participants who choose ‘injectable PrEP’ or ‘condoms and injectable PrEP’ when asked the question “If you wanted to protect yourself from getting HIV, which of the following product(s) would you prefer to use?”

9. SAFETY ANALYSES

See section 8.1 above. In addition to the primary safety outcomes (grade 2 or higher), AEs and laboratory data will be summarized in the closed DSMB report (described in the SPDSMP).

9.1 Adverse Events and Deaths

Adverse events of special interest (AESI) will be summarized in the Clinical Study Report. Planned AESI summaries for the CSR are described in Appendix A.

9.2 Laboratory Evaluations

Population: Safety population

Description: Laboratory findings for CBC (hemoglobin, platelets, WBC, neutrophils, lymphocytes), chemistries (urea, creatinine, CPK, glucose, calcium, phosphorous, amylase, lipase), liver function (AST, ALT, total bilirubin, alkaline phosphatase) and fasting lipid profile (total cholesterol, triglycerides, HDL, LDL) will be reported by grade, as defined in the “Division of AIDS (DAIDS) Table for Grading the Severity of Adult and Pediatric Adverse Events”. The proportion of laboratory findings qualifying as Grade 2 or above will be presented. Baseline laboratory values will be summarized by site using: median, 1st and 3rd quartiles, and min and max. Change from baseline in laboratory values will be summarized at follow up visits using: median, and 1st and 3rd quartile. Summaries involving values and changes from baseline at scheduled visit time points will consider values from scheduled visits only, and in the case of missing values, results will not be carried forward from interim (unscheduled) visits. For summaries and analyses involving changes in laboratory values over time or maximum change from baseline (e.g. shift tables), values from interim (unscheduled) visits will also be considered.

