### **7.7.6 Local Laboratory Values**

Box plots of local laboratory values will be generated for baseline values and for values measured during the course of the study by visit. Each box plot will show the first quartile, the median, and the third quartile. Outliers will also be plotted. If appropriate, horizontal lines representing boundaries for abnormal values will be plotted.

The number (percentage) of participants with local laboratory values recorded as meeting Grade 2 AE criteria or above as specified in the DAIDS AE Grading Table will be tabulated for follow-up time points. Reportable clinical laboratory abnormalities without an associated clinical diagnosis will also be included in the tabulation of AEs described above.

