### FOOTNOTES FOR APPENDIX I:

 Demographics may be collected and reported at either Screening or Enrollment.

 Staff are required to observe participants take one pill at Enrollment. If participants return with their pills at Weeks 2 & 4, staff will observe participant take one pill then as well, unless the participant has already taken oral study product that day. Participants must not be asked to take a second dose of oral study product for the sake of observation.

 Full physical exam is to be conducted during Enrollment. A targeted physical exam will be done at all other visits. Participant pulse, blood pressure and weight must be recorded at every visit. BMI must be calculated.

 The initial dose of the Hep B vaccination will ideally be given at Week 2, though there is flexibility around the timing of the vaccination. Subsequent doses may be given at different visits than indicated in this SOE, as long as sites follow manufacturer guideline timing.

 The HIV testing algorithm is provided in the SSP Manual. Testing for acute HIV must be negative and must be performed within the 14 days prior to enrollment of the participant. If HIV rapid testing is indicated, this testing may be performed in the clinic or the laboratory. At least one HIV assay result must be available and reviewed the same day as sample collection and before product is administered.

 Participants will be tested for Hepatitis B surface antibody (HBsAb), and Hepatitis B core antibody (HBcAb, total) at Screening or Enrollment. HbsAg and HCV Ab must be resulted and reviewed prior to enrollment.

 At Screening: Creatinine. At and after enrollment: BUN/urea, creatinine, CPK, calcium, phosphorous, glucose, amylase, and lipase.

 At Screening: ALT and TBili. At and after Enrollment: AST, ALT, total bilirubin, and alkaline phosphatase.

 Total cholesterol, HDL, triglycerides, and LDL (either calculated or measured). Participants must have fasted for at least 8 hours, preferably 12 hours, prior to sample collection. Do not collect or test if <8 hours fasting.

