## 12.2 APPENDIX II. SCHEDULE OF EVALUATIONS – INJECTION PHASE (STEP 2)

WEEKS in Study (shaded column = injection visit)	Wk 5	Wk 6	Wk 9	Wk 10	Wk 17	Wk 18	Wk 25	Wk 26	Wk 33	Wk 34
ADMINISTRATIVE, BEHAVIORAL, REGULATORY										
Locator information	X	X	X	X	X	X	X	X	X	X
HIV prevention counseling	X	X	X	X	X	X	X	X	X	X
Condoms per local SOC	X	X	X	X	X	X	X	X	X	X
Behavioral/Acceptability assessment (CASI)	X		X		X		X		X	
Qualitative interviews begin (approximately)										X
CLINICAL EVALUATIONS & PROCEDURES										
Adherence, risk reduction counseling	X	X	X	X	X	X	X	X	X	X
Medical history  , concomitant medications, targeted physical exam	X	X	X	X	X	X	X	X	X	X
Hep B vaccination (if needed) 		X								X
Blood collection	X	X	X	X	X	X	X	X	X	X
Urine collection	X	X	X	X	X	X	X	X	X	X
Rectal swab collection					X					X
Injections for all participants	X		X		X		X		X	
ISR evaluation		X		X		X		X		X
Step 3 product choice discussion									X	X
Interviewer administered product choice assessment										X
If product chosen is oral PrEP: Provision of Tenofovir/Emtricitabine (Trade name: TDF/FTC, Truvada®) (3 months' worth)										X
LOCAL LABORATORY EVALUATIONS & PROCEDURES										
HIV testing 	X	X	X	X	X	X	X	X	X	X
CBC with differential	X	X	X	X	X	X	X	X	X	X
Chemistry testing 	X	X	X	X	X	X	X	X	X	X
Liver function testing 	X	X	X	X	X	X	X	X	X	X
Fasting lipid profile 										X
Syphilis testing										X
GC/CT testing (urine, rectal, and oral pharyngeal swabs)					X				X	
Urinalysis (protein, glucose; at the clinic or local lab)	X	X	X	X	X	X	X	X	X	X
Plasma storage 	X	X	X	X	X	X	X	X	X	X

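### SAP 9.2 summarises glucose change from the Week 0 baseline without using fasting state, although a fast is scheduled at Week 0 and at only 1 of the 12 later Step 1–2 glucose draws

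*SAP*

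**What the plan says.** SAP 9.2 (Laboratory Evaluations, Safety population) lists glucose with the "chemistries (urea, creatinine, CPK, glucose, calcium, phosphorous, amylase, lipase" and attaches a fasting condition only to the lipids: "fasting lipid profile (total cholesterol, triglycerides, HDL, LDL) will be reported by grade". It then applies one rule to all of them: "Change from baseline in laboratory values will be summarized at follow up visits using: median, and 1st and 3rd quartile". For analyses of "maximum change from baseline (e.g. shift tables), values from interim (unscheduled) visits will also be considered". Protocol 7.7.6 adds a graphical version: "Box plots of local laboratory values will be generated for baseline values and for values measured during the course of the study by visit".

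The schedule comes from the protocol appendices. Appendix I, footnote 7, fixes the chemistry content: "At Screening: Creatinine. At and after enrollment: BUN/urea, creatinine, CPK, calcium, phosphorous, glucose, amylase, and lipase". Footnote 9 requires a fast of at least 8 hours for the lipid profile and adds: "Do not collect or test if <8 hours fasting". In Appendix II the row "Fasting lipid profile" has a single mark, in the last column (Week 34), while the chemistry row is marked at all ten visits. Neither document states a fasting rule for glucose or for the chemistry panel.

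**The concern.** Change from baseline is interpretable only if both values were taken under comparable conditions. For glucose, the visit that supplies the baseline has a scheduled fast and nearly all the visits compared with it do not. The imbalance follows time on treatment: there is a fast before the first dose, none through the rest of the oral phase and most of the injection phase, then one at Week 34.

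If fewer participants are fasting after Week 0, glucose would drift upward in this summary with no drug effect at all, and a single-arm trial has no comparator that would show the same drift. Glucose is also an analyte on which readers may look for a signal: SAP Appendix A lists hyperglycemia/new-onset diabetes as an adverse event of special interest, citing an observation in HPTN 083 and the drug class.

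**Working it through.** The plan states no figure on this point, so there is none to reproduce. The check is a count of scheduled visits.

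**Inputs**
- Baseline: Week 0. Screening chemistry is creatinine only (Appendix I, footnote 7), and the first dose is given at the end of the Week 0 visit (Protocol 5.2), so Week 0 is the only scheduled pre-dose glucose.
- Later Step 1 glucose: Weeks 2 and 4 (Appendix I), 2 draws.
- Step 2 glucose: Weeks 5, 6, 9, 10, 17, 18, 25, 26, 33 and 34 (Appendix II and its footnote 4), 10 draws.
- Step 3-injection glucose: +8, +24 and +48 (Appendix IV and its footnote 4), 3 draws, leaving aside the early-discontinuation visit.
- Step 3-oral PrEP: creatinine only (Appendix III, footnote 4), so no glucose.
- Scheduled fasts: Week 0 and Week 34. Appendices III and IV have no lipid row.
- Enrolled: nine (SAP 6.4).

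**Counts**
- Later Step 1–2 glucose draws: 2 + 10 = 12.
- With a scheduled fast: 1 (Week 34). Without: 12 − 1 = 11, and 11/12 = 92%.
- Adding Step 3-injection: 12 + 3 = 15 draws, of which 14 have no scheduled fast (14/15 = 93%).
- Step 1–2 values in nine participants: at most 9 × 12 = 108. At most 9 × 1 = 9 of these fall at a visit with a scheduled fast, and at most 9 × 11 = 99 do not.
- Possible Week 0 to Week 34 pairs fasting at both visits: 0 to 9.

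The Week 34 position is read from an extracted table. Appendix II, footnote 6, fits it, since it moves the lipid test for participants who have not completed five injections. If the mark belonged to another Step 2 visit, the count of 1 in 12 would be unchanged.

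**What the imbalance can do.** Let f0 be the share fasting at Week 0, ft the share fasting at a later visit, and d the mean difference between unfasted and fasted glucose, assumed positive and equal at both visits. With no drug effect, the expected change in the mean is

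(f0 − ft) × d.

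This is zero if the shares are equal, and reaches d if everyone fasts at Week 0 and no one does later. The SAP uses the median, which need not follow this formula exactly but moves for the same reason. The documents give none of f0, ft or d. They support only the expectation that f0 exceeds ft at visits without a scheduled fast.

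**The case against.** The strongest objection is that the fast does not govern glucose. A participant who arrives unfasted at Week 0 has lipids withheld, but nothing withholds the chemistry panel, and Protocol 5.2 does not require those results before enrollment. A reader might infer a fasted baseline set against unfasted follow-up; the documents do not establish that. Baseline may be mixed, and some participants may happen to be fasting at later visits. This objection stands. It reduces the likely shift, but it also means the reader cannot tell which baseline values are fasted, which is itself a reason for a flag.

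Second, no effect on a result is shown. A reader might infer that the primary safety endpoint or the hyperglycemia assessment is biased by this rule. Neither depends on it: SAP 8.1 counts abnormalities reported as adverse events, and SAP Appendix A identifies events of special interest by MedDRA preferred term, presents listings, and plans no formal comparison. This also stands.

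Third, the SSP Manual, the Chemistry Panel case report form and the DAIDS grading table are not among the documents, and any of them may deal with fasting. It would therefore be too strong to say that the trial ignores fasting. What can be said is that the SAP text makes no use of fasting state for glucose.

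Fourth, the remedy leaves little to analyse. That is true of the paired summary. It does not argue against labelling, which removes no planned output.

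**Conclusion.** The point holds as a minor analysis issue. SAP 9.2 compares glucose at a visit with a scheduled fast to glucose at visits of which 11 of 12 in Steps 1–2, and all 3 in Step 3-injection, have none. Baseline glucose is more likely to be fasted than follow-up glucose, and a rise from that cause could not be separated from a drug effect in this design. The by-visit box plots share the problem. So do the maximum-change and shift tables, which also admit unscheduled visits with no stated fast.

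The conclusion rests on two assumptions: that a scheduled lipid fast makes fasting more common at that visit, and that unfasted glucose tends to be higher. Whether a shift occurs, and how large it is, cannot be determined from the documents. The reach is one descriptive summary and its plots and tables in at most nine people. It is worth correcting because the correction is cheap, not because any endpoint is at risk.

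**What to change.** In SAP 9.2:

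1. Derive a fasting flag for each glucose value from the Chemistry Panel case report form, if that form records fasting status. Otherwise treat a glucose value as fasting when a completed fasting lipid form exists for the same visit, since lipids may not be collected after less than 8 hours.
2. Report glucose change from baseline for pairs flagged fasting at both visits. If the lipid form is the source, this is Week 0 to Week 34.
3. Keep the other glucose summaries, the Protocol 7.7.6 box plots and any maximum-change or shift table, but label them 'fasting status not established'.

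The cost is a few lines of SAP text and one derived variable, with no new data collection. The downside is 0 to 9 pairs at possibly a single time point, and the lipid-form fallback cannot sort fasted from unfasted values at the other 11 Step 1–2 visits. Participants who leave injections early and move to oral PrEP add no pair under the fallback. Their lipid test moves to the first visit after the switch, and Appendix III schedules no chemistry at +8 and creatinine only at later visits, so no glucose accompanies that fast.

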9.3 Other Safety Measures

10. IMMUNOGENICITY ANALYSES

NA

11. PHARMACOKINETIC ANALYSES

Plasma will be collected during Steps 1 and 2 for pharmacologic assessment of CAB concentrations. Plasma and DBS will also be collected in Step 3, and if a study participant seroconverts, for potential pharmacologic analysis of plasma TFV and DBS TFV-DP concentrations, respectively, to assess PrEP adherence, and for potential HIV genotyping. Analysis details are provided in the current version of the Pharmacokinetics Analysis Plan

12. SECONDARY ANALYSES

For binary secondary endpoints, the number and proportion of endpoints will be computed along with corresponding 95% confidence intervals. Each summary will be provided both overall and by site. CSR analysis will be only summarized overall. Endpoint descriptions are available in section 2.2.

12.1 Plasma CAB pharmacokinetics

Analysis details are provided in the current version of the Pharmacokinetics Analysis Plan

12.2 Proportion of participants experiencing Grade 2 or higher clinical AEs and laboratory abnormalities in the oral phase and over the entire study period

Cohort: Safety population

Analysis description: Number and percent of participants experiencing any Grade 2 or higher clinical adverse events (AEs) or laboratory abnormalities from:

1. enrollment to week 5 (oral phase (step 1), including interim visits).
2. enrollment to 8 weeks following the last injection received (aggregate over oral+injection phases (step 1-step 2) including interim visits)

12.3 Proportion of participants receiving one or more injections who experience Grade 2 or higher clinical AEs and laboratory abnormalities from initial injection to 36 weeks later

Population: Injection population

Analysis description: Number and percent of participants experiencing any Grade 2 or higher clinical adverse events (AEs) or laboratory abnormalities from the first injection visit to approximately 36 weeks later regardless of whether participants received all 5 injections. For participants receiving all 5 injections, the end date is 8 weeks following the week 33 injection visit. For participants discontinuing study product early and moving on to Step 3, the end date is 36 weeks after the initial injection. Participants who terminate early are included in the analysis and censored at the date of termination.

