### 7.8.2 Safety Endpoints

Secondary safety analyses will be summarized using the same method described in section 7.7.1, applied over the oral phase only (week 0 to week 4) and the aggregate oral+injectable+follow-up period.

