2.1 General Design Considerations

HPTN083-01 is a phase IIB single arm trial designed to establish the minimum safety, tolerability and acceptability data needed to support the use of cabotegravir long-acting injection (CAB LA) in an adolescent population, potentially transforming the field of HIV prevention for young people. The study target population is sexually active, healthy male adolescents aged below 18 years. The study target is to enroll more than 50 participants with at least 50 participants receiving at least one injection. Participant recruitment will take approximately 12 months.

Study participation includes Step 1: a 5-week oral CAB 30mg QD safety lead-in followed by Step 2: a series of 5 intramuscular (IM) injections of 3 mL (600 mg) cabotegravir administered at 8-week intervals after a 4-week loading dose (injections at weeks 5, 9, 17, 25 & 33). Adherence support strategies (e.g., counseling, reminders, pill cases) will be included to support pill-taking during the first five weeks and to support retention during the injectable phase. A safety visit will follow each injection to ascertain pharmacokinetic-peak safety data, including injection site reactions. Step 3: A blood draw visit, the +8 Week Visit, will follow the week 33 injection to monitor CAB drug levels. All participants who have received at least one injection will be followed for 48 weeks after their last injection. Waning levels of cabotegravir (the PK tail) will be covered with locally sourced oral TENOFOVIR/EMTRICITABINE (TRADE NAME: TDF/FTC, TRUVADA®) for daily use for 48 weeks. In Step 3 participants may also choose to continue with 8-week dosing of injectable of CAB-LA for 48 weeks (5 additional injections beyond the initial 5 injections, administered at weeks +8, +16, 24, +32, +40, and +48.) Behavioral and acceptability data will be collected via computer-assisted self-interview (CASI). Total participant commitment for the entire study is up to 87 weeks, or approximately 1.5 years. We anticipate recruitment for the study will take approximately 12 months.

Participants who discontinue study product during Step 2 for any reason other than HIV infection or AE occurrence will be transitioned to open label TDF-FTC for 48 weeks.

There are in total three study sites:

- Adolescent and Young Adult Research at the Core Center (AYAR at CORE), Chicago, IL;
- St. Jude Children's Research Hospital CRS, Memphis, TN;
- Fenway Health CRS, Boston, MA.

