3. GENERAL DATA ANALYSIS CONSIDERATIONS

3.1 Analysis Set(s)

Primary and secondary analyses will be carried out among the following populations:

Screened Population: Includes all participants who were screened for potential enrollment.

Injection Population: Includes enrolled participants who receive at least one injection of CAB LA.

Safety Population: Includes enrolled participants who began step 1 (oral phase).

Enrolled Population: Includes all enrolled participants.

Seroconverter Population: Includes all enrolled participants who seroconverted during the study.

TDF/FTC Population: All enrolled participants who were provided TDF/FTC during the study.

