8.1 Safety endpoint analysis

Cohort: Injection population

Analysis description: Number and percent of participants experiencing any Grade 2 or higher clinical adverse events (AEs) or laboratory abnormalities (reported as adverse events) from the first injection visit to 8 weeks after the last Step 2 injection visit, or Week 41, whichever comes first. See Section 3.2 for details regarding aggregation and tabulation of AEs.

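### SAP 12.2 item 2 ends the aggregate safety window at the last injection of any kind but labels it Steps 1–2, so its end date is contradictory and, read literally, depends on Step 3 product choice

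*SAP*

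**What the plan says.** SAP 12.2 covers Grade 2 or higher clinical AEs and laboratory abnormalities "in the oral phase and over the entire study period". Its cohort is the Safety population, which SAP 3.1 defines thus: "Includes enrolled participants who began step 1 (oral phase". Item 2 runs the aggregate window from "enrollment to 8 weeks following the last injection received (aggregate over oral+injection phases (step 1-step 2) including interim visits".

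Other places bear on where that window ends:

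- SAP 2.1: "In Step 3 participants may also choose to continue with 8-week dosing of injectable of CAB-LA for 48 weeks". Protocol 5.7 also lets a participant on TDF/FTC switch to CAB LA during Step 3.
- SAP 8.1, the primary safety window, runs "from the first injection visit to 8 weeks after the last Step 2 injection visit, or Week 41, whichever comes first".
- SAP 12.3 ends 8 weeks after the week 33 injection for those who receive all five injections, and 36 weeks after the first injection for those who stop early.
- The SAP 2.2 secondary objective speaks of the combined oral and injectable period. The endpoint lists in SAP 2.2 and Protocol 7.2.2 speak of the whole study period.
- Protocol 7.8.2 has the secondary safety analyses "applied over the oral phase only (week 0 to week 4"), and then over the oral, injectable and follow-up periods combined.

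**The concern.** Item 2 does not say which injection sets the end date. SAP 8.1 and 12.3 both do, and both name Step 2 injections. Once Step 3 offers further CAB LA, the last injection a participant receives may be a Step 3 injection. The stated end date then lies outside the phases that the same line says it covers.

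A programmer could defend two derivations. One stops at the last Step 2 injection plus 8 weeks, following the label. The other stops at the last injection of any kind plus 8 weeks, following the rule. Under the second, follow-up length is set partly by what the participant chooses to take after Step 2. The resulting proportion mixes short and long periods at risk without saying so. Neither derivation gives the aggregate through follow-up that Protocol 7.8.2 asks for in every participant.

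**Working it through.** **Inputs.** Step 2 injections at Weeks 5, 9, 17, 25 and 33 (SAP 2.1, Protocol 2.3). Step 3 CAB LA times of +8, +16, +24, +32, +40 and +48 weeks (SAP 2.1, Protocol Appendix IV). Follow-up of 48 weeks after the last Step 2 injection (Protocol 2.3). Enrolment stopped at nine (SAP 6.4).

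**The plan's own figures.** The last Step 2 injection plus 8 weeks is 33 + 8 = Week 41, as in SAP 8.1. From the first injection that is 41 − 5 = 36 weeks, as in SAP 12.3. Both reproduce.

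**Planned end of follow-up.** For a five-injection completer, 33 + 48 = Week 81.

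**Literal rule: end = week of last injection received + 8.**

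| Injection history | Last injection | Literal end |
|---|---|---|
| Never injected | none | not stated |
| 1 injection, none in Step 3 | Week 5 | Week 13 |
| 2 injections, none in Step 3 | Week 9 | Week 17 |
| 3 injections, none in Step 3 | Week 17 | Week 25 |
| 4 injections, none in Step 3 | Week 25 | Week 33 |
| 5 injections, none in Step 3 | Week 33 | Week 41 |
| 5 injections, last Step 3 injection at +8 | Week 41 | Week 49 |
| … at +16 | Week 49 | Week 57 |
| … at +24 | Week 57 | Week 65 |
| … at +32 | Week 65 | Week 73 |
| … at +40 | Week 73 | Week 81 |
| … at +48 | Week 81 | Week 89, cut at Week 81 |

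SAP 2.1 says five additional injections but lists six times, which must be reconciled. The longest window here is Week 81 either way. The Step 3 rows are for completers. An early discontinuer who takes CAB LA in Step 3 has a Step 3 clock that starts earlier, so the weeks differ, but the window still extends past the Step 2 end date.

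**Label reading (Steps 1–2 only).** Completers end at Week 41 whatever they take in Step 3. Early discontinuers end at Weeks 13 to 33, as in the table.

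**Largest difference between readings for a completer.** 81 − 41 = 40 weeks; 81/41 = 1.98.

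**Illustration of event risk.** The documents give no base rate, so p, the chance of an event by Week 41, is assumed, with a constant hazard. Risk by week w is 1 − (1 − p)^(w/41).

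| Assumed p by Week 41 | By Week 13 | By Week 81 |
|---|---|---|
| 20% | 7% | 36% |
| 40% | 15% | 64% |
| 80% | 40% | 96% |

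The Week 81 column is the upper end. It supposes CAB LA is taken to the end of Step 3, and laboratory testing is sparser in Step 3 (Protocol Appendices III and IV) than in Step 2 (Appendix II).

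**Weight of one participant.** 1/9 = 11.1 percentage points, if all nine enrolled are in the Safety population.

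**Oral window (minor).** SAP 12.2 item 1 ends at week 5 and Protocol 7.8.2 at week 4. SAP 8.1 opens at the first injection visit. An event between Week 5 and a late first injection falls in neither phase-specific window, although item 2 still counts it for a participant who is then injected.

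**The case against.** The strongest reply is that the bracket settles the matter. The line restricts itself to Steps 1–2, the SAP 2.2 objective says oral plus injectable, and SAP 12.4 counts at most five injections per participant. On that evidence the authors probably meant Step 2 injections. This stands as far as it goes: a reader might infer that the SAP definitely follows CAB LA continuers through Step 3, and the documents do not support that. The defect is a contradiction between a rule and its label. The bracket does not remove it, because the 12.2 heading, both endpoint lists and Protocol 7.8.2 point to a longer period.

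Other parts of the reply also stand:

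- A reader might infer that everyone who does not continue CAB LA stops near Week 41. That is true only of five-injection completers.
- A reader might infer that 8.1 was updated for the Step 3 option and 12.2 overlooked. SAP version 1.0 is not available, and the change history lists Section 12 among the revised sections.
- Participants never injected have no stated end date, but Protocol 5.4.1 ends their follow-up, so in practice study exit closes their window.
- SAP 12.2 was never directly comparable with 8.1 or 12.3, since its start date and population differ by design.
- This is a descriptive secondary summary in a single-arm trial that stopped at nine enrolled, and 12.3 already gives a window of about 36 weeks for injected participants.

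**Conclusion.** The concern holds as an internal contradiction in a stated end-date rule, together with a departure from the protocol's aggregate period. It does not hold as a settled Step 3 window.

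Under the literal rule the window for a completer is 8 to 40 weeks longer with Step 3 CAB LA than without it, at most 1.98 times as long. Among participants with no Step 3 injection it ranges from 13 to 41 weeks. These figures rest on the nominal visit schedule and on follow-up ending at Week 81 for completers. The event-risk figures rest further on an assumed base rate and a constant hazard, and are an upper-end illustration. The documents do not show how many participants chose CAB LA in Step 3, so the number whose classification could change is unknown; each would move the proportion by about 11 points if all nine are analysed.

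The change should be made: the rule decides which events are counted in a listed secondary safety endpoint, and the endpoint cannot be reproduced from the SAP as it stands. The never-injected and oral-window points are minor.

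**What to change.** 1. Define the Step 1–2 aggregate with an end that does not depend on Step 3 choice. Either use 8 weeks after the last Step 2 injection, capped at Week 41, as in SAP 8.1; or, if equal time at risk is wanted, use about 36 weeks after the first injection, as in SAP 12.3. The first option still leaves early discontinuers at Weeks 13 to 33. The second brings all injected participants who remain in follow-up to about Week 41. For Safety population members never injected, use study exit.
2. Report separately the protocol's aggregate over the oral, injectable and follow-up periods, to the end of follow-up, with Step 3 events shown by Step 3 product. Align the 12.2 heading and the SAP 2.2 objective and endpoint with whichever windows are reported.
3. As a minor point, end the oral window at the first injection, or at Step 1 exit, so that it meets the 8.1 window, and reconcile week 5 with the protocol's week 4.

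The cost is about one sentence per window, a change to the end-date derivation and one further table. No new data are needed, since Protocol 6.1 already collects AEs until follow-up ends.
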